## 8. Design

### 8.1. Scale and Duration

The REPRISE II clinical study is a prospective, single-arm, multicenter study designed to evaluate the safety and performance of the Lotus Valve System for TAVR in symptomatic subjects who have severe calcific aortic valve stenosis and who are at high risk for surgical valve replacement.

All subjects implanted will be followed at baseline, peri- and post-procedure, at discharge or 7 days post-procedure (whichever comes first), 30 days, 3 months, 6 months, and then annually for up to 5 years post-procedure. Subjects who do not have the Lotus Valve implanted will be assessed through 30 days post procedure for safety/adverse events.

The REPRISE II study will be conducted in accordance with the International Standard ISO 14155: 2011; ethical principles that have their origins in the Declaration of Helsinki; the relevant parts of the International Conference on Harmonisation (ICH) Guidelines for Good Clinical Practices (GCP); and pertinent individual country/state/local laws and regulations. See Section 11 below for additional information on study design and data collection.

## **8.2. Treatment Assignment**

Screening materials from eligible subjects who are identified by the investigators as having met the inclusion and exclusion criteria (see below Table 9.2-1 and Table 9.3-1, respectively) and who provide written informed consent, will be reviewed by a Case Review Committee (CRC, see Section 22.2) to assess and confirm suitability of subjects for enrollment. ***In all enrolled subjects an attempt will be made to implant a single Lotus Valve.***

### **8.2.1. Treatment**

The test device is the Lotus Valve System, which consists of a bioprosthetic bovine pericardial aortic valve and a delivery system. The commercially available Lotus Introducer Set is used as an accessory in the procedure. See Section 5 for a detailed description and information on device sizes.

## **8.3. Study Design Justification**

In order to support the stated objectives of this study (see Section 6) while also limiting the potential exposure of study subjects to risk, a total of 120 subjects will be enrolled in the main trial cohort at up to 15 centers in these possible countries: Australia, France, Germany and United Kingdom. Planned interim analyses based on the primary endpoint at 30 days post-implant procedure will be performed on the first 40 and 60 enrolled subjects and a final analysis will be conducted on the main trial cohort (N=120). Subsequently, up to 130 additional subjects will be enrolled at up to 21 centers in Australia and European countries and a statistically powered analysis based on the primary safety endpoint will be performed on the combined main and extended trial cohort (250 subjects). In addition to the risk-benefit analysis noted in Section 4.2 (see also Section 19), ongoing dynamic data safety monitoring will be performed throughout the trial to minimize risk to subjects. All implanted subjects will be followed for 5 years post index procedure.

## **9. Subject Selection**

### **9.1. Study Population and Eligibility**

The study will include subjects presenting with symptomatic, calcific aortic valve stenosis who are considered at high risk for surgical valve replacement. Prior to being eligible for the REPRISE II study, a subject must meet all of the inclusion criteria (Section 9.2) and none of

the exclusion criteria (Section 9.3). All subjects will then be reviewed by the CRC to confirm eligibility and suitability for enrollment in the study.

## 9.2. Inclusion Criteria

Subjects who meet all of the following criteria (see Table 9.2-1) may be given consideration for inclusion in this clinical investigation, provided no exclusion criterion (see Section 9.3) is met.

**Table 9.2-1: Inclusion Criteria**

Inclusion Criteria	
IC1.	Subject is $\geq 70$ years of age
IC2.	Subject has documented calcific native aortic valve stenosis with an initial aortic valve area (AVA) of $< 1.0 \text{ cm}^2$ (or AVA index of $< 0.6 \text{ cm}^2/\text{m}^2$ ) and either a mean pressure gradient $> 40 \text{ mm Hg}$ or a jet velocity $> 4 \text{ m/s}$ , as measured by echocardiography.
IC3.	Subject has a documented aortic annulus size between $\geq 20$ and $\leq 27 \text{ mm}$ based on pre-procedure diagnostic imaging
IC4.	Subject has symptomatic aortic valve stenosis with NYHA Functional Class $\geq \text{II}$ .
IC5.	Subject is considered high risk for surgical valve replacement based on at least one of the following:
	– STS score $\geq 8\%$ , and/or
IC6.	– Agreement by the heart team (which must include an in-person evaluation by an experienced cardiac surgeon) that subject is at high operative risk of serious morbidity or mortality with surgical valve replacement.
IC6.	Heart team (which must include an experienced cardiac surgeon) assessment that the subject is likely to benefit from valve replacement
IC7.	Subject (or legal representative) understands the study requirements and the treatment procedures, and provides written informed consent.
IC8.	Subject, family member and/or legal representative agree(s) and subject is capable of returning to the study hospital for all required scheduled follow up visits.

Abbreviations: AVA=aortic valve area; NYHA=New York Heart Association; STS= Society of Thoracic Surgeons

## 9.3. Exclusion Criteria

Subjects who meet any one of the following criteria (Table 9.3-1) will be excluded from this clinical study.

**Table 9.3-1: Exclusion Criteria**

Exclusion Criteria	
EC1.	Subject has a congenital unicuspid or bicuspid aortic valve.
EC2.	Subject with an acute myocardial infarction within 30 days of the index procedure (defined as Q-wave MI or non-Q-wave MI with total CK elevation $\geq$ twice normal

Table 9.3-1: Exclusion Criteria

	in the presence of CK-MB elevation and/or troponin level elevation).
EC3.	Subject has had a cerebrovascular accident or transient ischemic attack within the past 6 months, or has any permanent neurologic defect prior to study enrollment.
EC4.	Subject is on dialysis or has serum creatinine level >3.0 mg/dL or 265 µmol/L.
EC5.	Subject has a pre-existing prosthetic heart valve (aortic or mitral) or a prosthetic ring in any position.
EC6.	Subject has ≥3+ mitral regurgitation, ≥3+ aortic regurgitation or ≥3+ tricuspid regurgitation (i.e., subject cannot have more than moderate mitral, aortic or tricuspid regurgitation).
EC7.	Subject has a need for emergency surgery for any reason.
EC8.	Subject has a history of endocarditis within 12 months of index procedure or evidence of an active systemic infection or sepsis.
EC9.	Subject has echocardiographic evidence of intra-cardiac mass, thrombus or vegetation.
EC10.	Subject has Hgb <9 g/dL, platelet count <50,000 cells/mm  or >700,000 cells/mm  , or white blood cell count <1,000 cells/mm  .
EC11.	Subject is receiving chronic (≥72 hours) anticoagulation therapy (e.g., warfarin, dabigatran, etc.), and cannot tolerate concomitant therapy with aspirin or clopidogrel (subjects who require chronic anticoagulation must additionally be able to be treated with either aspirin or clopidogrel).*
EC12.	Subject has active peptic ulcer disease or gastrointestinal bleed within the past 3 months, other bleeding diathesis or coagulopathy or will refuse transfusions.
EC13.	Subject has known hypersensitivity to contrast agents that cannot be adequately pre-medicated, or has known hypersensitivity to aspirin, all thienopyridines, heparin, nickel, titanium, or polyurethanes.
EC14.	Subject has a life expectancy of less than 12 months due to non-cardiac, co-morbid conditions based on the assessment of the investigator at the time of enrollment.
EC15.	Subject has hypertrophic obstructive cardiomyopathy.
EC16.	Subject has any therapeutic invasive cardiac procedure (including balloon aortic valvuloplasty) within 30 days prior to the index procedure (except for pacemaker implantation which is allowed).
EC17.	Subject has untreated coronary artery disease, which in the opinion of the treating physician, is clinically significant and requires revascularization.
EC18.	Subject has documented left ventricular ejection fraction <30%.
EC19.	Subject is in cardiogenic shock or has hemodynamic instability requiring inotropic support or mechanical support devices.
EC20.	Subject has severe peripheral vascular disease (including aneurysm defined as maximal luminal diameter >5 cm or with documented presence of thrombus, marked tortuosity, narrowing of the abdominal aorta, severe unfolding of the thoracic aorta or thick [>5 mm] protruding or ulcerated atheroma in the aortic arch) or symptomatic carotid or vertebral disease.
EC21.	Femoral artery lumen of <6.0 mm for subjects requiring 23 mm valve size or <6.5 mm for subjects requiring 27 mm valve size, or severe iliofemoral tortuosity or calcification that would prevent safe placement of the introducer sheath.
EC22.	Current problems with substance abuse (e.g., alcohol, etc.).

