	
EC10. Subject has Hgb <9 g/dL, platelet count <50,000 cells/mm^3 or >700,000 cells/mm^3, or white blood cell count <1,000 cells/mm^3.
 
EC11. Subject requires chronic anticoagulation therapy (e.g., warfarin, dabigatran, etc.) and cannot tolerate concomitant therapy with either aspirin or clopidogreld.
 
Note: Subjects who require chronic anticoagulation must be able to be treated additionally with either aspirin or clopidogreld.
 
EC12. Subject has active peptic ulcer disease or gastrointestinal bleed within the past 3 months, other bleeding diathesis or coagulopathy or will refuse transfusions.
 
EC13. Subject has known hypersensitivity to contrast agents that cannot be adequately pre-medicated, or has known hypersensitivity to aspirin, all thienopyridines, heparin, nickel, tantalum, titanium, or polyurethanes.
 
EC14. Subject has a life expectancy of less than 12 months due to non-cardiac, co-morbid conditions based on the assessment of the investigator at the time of enrollment.
 
EC15. Subject has hypertrophic obstructive cardiomyopathy.
 
EC16. Subject has any therapeutic invasive cardiac procedure (including balloon aortic valvuloplasty) within 30 days prior to the index procedure (except for pacemaker implantation which is allowed).
 
EC17. Subject has untreated coronary artery disease, which in the opinion of the treating physician is clinically significant and requires revascularization.
 
EC18. Subject has documented left ventricular ejection fraction <30%.
 
EC19. Subject is in cardiogenic shock or has hemodynamic instability requiring inotropic support or mechanical support devices.
 
EC20. Subject has severe peripheral vascular disease (including aneurysm defined as maximal luminal diameter >5 cm or with documented presence of thrombus, marked tortuosity, narrowing of the abdominal aorta, severe unfolding of the thoracic aorta or thick [>5 mm], protruding or ulcerated atheroma in the aortic arch) or symptomatic carotid or vertebral disease.
 
EC21. Femoral artery lumen of <6.0 mm for subjects requiring 23 mm valve size or <6.5 mm for subjects requiring 27 mm valve size, or severe iliofemoral tortuosity or calcification that would prevent safe placement of the introducer sheath.

--	--

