## 4. Introduction

This protocol specifies procedures and contains information relevant to the clinical evaluation of the Lotus™ Valve System, a transfemoral aortic valve replacement device designed and manufactured by Boston Scientific Structural Heart a Division of Boston Scientific Corporation. The Lotus Valve System consists of a pre-loaded, stent-mounted tissue valve prosthesis and catheter delivery system designed to enable predictable and precise placement of the valve during transcatheter aortic valve replacement (TAVR). Early leaflet function during valve deployment and the presence of a radiopaque tantalum marker on the braided frame facilitates optimal initial positioning of the valve. If needed, the valve may be un-locked after being locked and partially or fully resheathed for repositioning prior to final release or can be fully retrieved if during the procedure the decision is made not to implant. The valve also has a polyurethane outer seal (Adaptive™ Seal) designed to minimize paravalvular leakage. Additional device information can be found in Section 5.

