### 5.1.1. Lotus Valve

The Lotus Valve (Figure 5.1-2) consists of 3 bovine pericardial leaflets. The commissures of the leaflets are attached to the valve frame through portions of the locking components.

The valve frame is made of a single nitinol wire strand woven into a braided structure. The wire ends of this frame are encapsulated by a tantalum crimp that is used as a radiopaque marker, and which is located in the center of the frame height. The braided structure is designed to foreshorten and expand radially when delivered, and is then locked in this position using a post and buckle locking mechanism.

The Adaptive™ Seal is made of a polyurethane/polycarbonate blend and is located on the outside bottom half of the frame. This seal provides a barrier between the native annulus and the frame to help reduce paravalvular leakage.

The valve is deployed in a beating heart and rapid pacing is not required during valve deployment. The valve begins to function early in the deployment process, providing stabilized hemodynamic functionality.

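### Exclusion criterion EC13 names tantalum hypersensitivity in the Synopsis but not in Table 9.3-1, the list the eligibility sections point to

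*Combined protocol and SAP*

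**What the plan says.** EC13 is stated in two places, both current protocol text. In the Synopsis (Section 2, Exclusion Criteria) it excludes a subject with a contrast sensitivity that cannot be managed by pre-medication "or has known hypersensitivity to aspirin, all thienopyridines, heparin, nickel, tantalum, titanium, or polyurethanes". In Table 9.3-1 (Section 9.3) the corresponding words are "or has known hypersensitivity to aspirin, all thienopyridines, heparin, nickel, titanium, or polyurethanes".

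The body of the protocol applies the table. Section 9.3 introduces it with "Subjects who meet any one of the following criteria (Table 9.3-1) will be excluded from this clinical study". Section 8.2 describes eligible subjects as "having met the inclusion and exclusion criteria (see below Table 9.2-1 and Table 9.3-1, respectively". Section 9.2 allows consideration for inclusion "provided no exclusion criterion (see Section 9.3) is met".

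Tantalum is part of the implant. Section 4 mentions "the presence of a radiopaque tantalum marker on the braided frame", and Section 5.1.1 says "The wire ends of this frame are encapsulated by a tantalum crimp that is used as a radiopaque marker". Section 19.1 lists allergic reaction among the potential adverse events and names device materials as one of the causes.

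**The concern.** An exclusion criterion should read the same wherever the protocol states it. Here the version the eligibility sections rely on is the shorter one, and the missing word names a material in a permanent implant. A site working from the Synopsis would exclude a patient with known tantalum hypersensitivity. A site working from Table 9.3-1 would find no criterion that does so.

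There is a compliance question as well. Section 15 forbids investigators to deviate from the protocol except in an emergency. With two texts and no rule of precedence, the document does not settle whether enrolling such a patient would be a deviation. Section 19.2 counts clear definition of the inclusion and exclusion criteria among the risk-mitigation measures, and two versions of EC13 do not serve that aim.

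**Working it through.** No formula applies. The check is a word-for-word comparison of the two EC13 texts, followed by a look at which text the rest of the protocol uses.

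**Step 1. The named sensitivities, after the contrast-agent clause, which is the same in both.**

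| Named item | Synopsis EC13 | Table 9.3-1 EC13 |
|---|---|---|
| Aspirin | yes | yes |
| All thienopyridines | yes | yes |
| Heparin | yes | yes |
| Nickel | yes | yes |
| Tantalum | yes | **no** |
| Titanium | yes | yes |
| Polyurethanes | yes | yes |
| Total | 7 | 6 |

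The difference is 7 − 6 = 1 item. Nothing appears in the table that is not also in the Synopsis.

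**Step 2. Is either text superseded or damaged?** Neither comes from the amendment log. The change tables in Section 27.1, as available for this review, record edits to EC1, EC11, EC16, EC17 and EC24 but none to EC13, so they do not show a deliberate change. The sentence in Table 9.3-1 is complete and grammatical with no redaction mark, which makes a fault in text extraction unlikely.

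**Step 3. Which list does the protocol apply?** Section 8.2 and the lead-in to Section 9.3 name Table 9.3-1. Sections 9.1 and 9.2 point to Section 9.3. That is four pointers to the list without tantalum and none to the Synopsis.

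**Step 4. Does the device description settle the intended wording?** It makes tantalum relevant but does not decide the matter. Section 5.1.1 also describes bovine pericardial leaflets and a seal made of a polyurethane and polycarbonate blend. Neither EC13 text names bovine tissue or polycarbonate, so EC13 was not written as a full list of implant materials.

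**The case against.** The wording difference itself cannot be disputed. The case against goes to its weight.

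- **Both texts can be obeyed at once.** Section 9.2 is permissive, and nothing in Table 9.3-1 obliges a site to enrol a tantalum-sensitive patient. A site that excludes the patient satisfies both lists. This is true, but a site following the table has no stated reason to exclude, so the texts can still lead to different decisions.
- **The count of pointers proves little.** Two of the four are lead-ins to the criteria tables themselves, and body sections normally cite body tables. Sections 10.1 and 12.2.2, which deal with enrolment and eligibility, cite neither list. This is fair. The count shows only which list a reader is directed to, and it would not matter if the lists agreed.
- **Other safeguards stand in the way.** The Case Review Committee confirms both eligibility and suitability (Section 9.1) and includes the sponsor for device expertise (Section 22.2). Operators must follow the Instructions for Use (Section 11.7.3), and training covers their contra-indications (Section 17.4.1). These lower the practical risk. However, the documents do not say which EC13 text the committee applies, and the Instructions for Use were not available for this review.
- **EC13 is one example of wider drift.** EC11 also differs: the Synopsis speaks of subjects who require chronic anticoagulation, the table of subjects already receiving it for at least 72 hours. That is a reason to check both lists together. It does not excuse the EC13 mismatch.

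**Conclusion.** The inconsistency is real: one named hypersensitivity is in the Synopsis and absent from the table that the eligibility text applies. Confidence is high in the wording difference. It does not extend to any measured effect on patients, because the documents give no frequency of tantalum hypersensitivity; the judgement that few patients would be affected is an assumption. Sample size, power, alpha and both primary endpoints are untouched. The point is minor in weight but worth correcting, because it concerns who may receive a permanent implant containing the material in question.

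**What to change.** Reconcile EC13 in the Synopsis and in Table 9.3-1 so that the two read identically. The sponsor should decide the wording with the device description in Sections 4 and 5.1.1 in view; this review takes no position on which version is right. It would be sensible to compare the remaining criteria in the two lists at the same time, since EC11 also differs.

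The cost is a text correction to one EC13 entry in the next amendment. No sample size or analysis changes. Any effect on enrolment is likely to be small, though the documents give no figure for it.

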**Table 9.3-1: Exclusion Criteria**

	
EC23. Subject is participating in another investigational drug or device study that has not reached its primary endpoint.
 
EC24. Subject has untreated conduction system disorder (e.g., Type II second degree atrioventricular block) that in the opinion of the treating physician is clinically significant and requires a pacemaker implantation.

--	--

\* An alternative P2Y12 inhibitor (e.g., ticlopidine) may be prescribed if subject is allergic to or intolerant of clopidogrel.

Abbreviation: AV= atrioventricular; CK=creatinine kinase; MI=myocardial infarction

## 10. Subject Accountability

### 10.1. Point of Enrollment

Subjects confirmed eligible for the study by the CRC (see Section 22.2) and who provided written informed consent are considered enrolled in the study as soon as an attempt is made to insert the Lotus Valve System into the subject's femoral artery.

### 10.2. Withdrawal

All subjects enrolled in the clinical study (including those withdrawn from the clinical study or lost to follow-up) shall be accounted for and documented. If a subject withdraws from the clinical investigation, the reason(s) shall be reported. If such withdrawal is due to problems related to investigational device safety or performance, the investigator shall ask for the subject's permission to follow his/her status/condition outside of the clinical study.

## 11. Study Methods

### 11.1. Data Collection

The study event schedules are shown diagrammatically and discussed in Figure 11.1-1 and Table 11.1-1 for the main trial cohort (N=120) and in Figure 11.1-2 and Table 11.1-2 for the subsequently enrolled 130 additional subjects (extended trial cohort).

[figure not shown]

Figure 11.1-1: REPRISE II Study Design – Main Trial Cohort

Table 11.1-1: Study Event Schedule – Main Trial Cohort

Assessment	Screening a	Baseline b	Procedure	Within 1 Day Post-procedure	Prior to Discharge or 7 Days Post-Procedure	30 Days c (±7 Days) Office Visit	3 Months c (±14 Days) Office Visit	6 Months c (±30 Days) Office Visit	12 Months c (±45 Days) Office Visit	24–60 Months c [Annual] (±45 Days) Office Visit
Signed Informed Consent Form d	X									
Demographics and medical history, including cardiac, neurological, renal (e.g., creatinine) and peripheral disease	X									
NYHA Classification	X				X	X	X	X	X	X
Neurological physical exam e		X			X				X	
NIHSS e		X			X				X	
Modified Rankin Scale e		X			X	X	X	X	X	X
12-lead ECG f	X	X	X f	X	X	X	X	X	X	
Laboratory tests g		X		X		X				
Risk assessments h	X									
Frailty, disability and comorbidity i		X							X	
Antiplatelet and other cardiovascular medications	X		X		X	X	X	X	X	X
TTE j	X				X	X	X	X	X	X
TEE k			X							
Coronary angiogram l	X									
CT angiogram of aortic structure m	X									

Table 11.1-1: Study Event Schedule – Main Trial Cohort

Assessment	Screening a	Baseline b	Procedure	Within 1 Day Post-procedure	Prior to Discharge or 7 Days Post-Procedure	30 Days c (±7 Days) Office Visit	3 Months c (±14 Days) Office Visit	6 Months c (±30 Days) Office Visit	12 Months c (±45 Days) Office Visit	24–60 Months c [Annual] (±45 Days) Office Visit
CT angiogram or invasive angiogram of iliofemoral system n	X									
Annual imaging (rotational X-ray) o									X	X
QOL surveys p		X				X		X	X	X q
Procedural cine-angiography (including post-deployment aortogram) r			X							
AE and ADE assessments s			X	X	X	X	X	X	X	
Device deficiencies, SAE, SADE, USADE, and CEC event assessment t			X	X	X	X	X	X	X	X

a: It is recommended that screening occur no later than 10 days prior to the index procedure (unless otherwise specified); results from these assessments should be submitted to the CRC at least 10 days prior to the planned procedure to allow for adequate scheduling of subject review at a CRC meeting.

b: Within 30 days prior to index procedure (unless otherwise specified)

c: All follow-up dates will be calculated from the date of the index procedure. Visits must be an office/clinical visit, but may be done in-hospital should the subject be admitted at the time. Subjects who are enrolled but do not receive a Lotus Valve will be followed for 30 days to assess for safety but do not need to have protocol required TTE, ECG, or laboratory tests or complete quality of life questionnaires.

d: Study-specific consent includes screening consent to perform required assessments that will be evaluated by the CRC to confirm subject eligibility. If the study Informed Consent Form is modified during the course of the study, study subjects will be re-consented as necessary.

e: Neurological physical examination must be performed by a neurologist or neurology fellow. NIHSS and mRS must be performed by certified personnel (external certification for NIHSS; internal or external certification for mRS). The assessors should be independent (not involved with the care of study subjects). For subjects diagnosed with a neurological event (e.g., stroke, transient ischemic attack), a neurological physical exam, mRS, and NIHSS must be performed after the event; mRS must also be administered at 90 days post-neurological event.

f: All baseline and post-procedure 12-lead ECGs must be performed according to the ECG Core Laboratory guidelines (see study Manual of Operations). Heart rhythm

